#### Background

In a proportion of fetuses with aortic valve stenosis the cardiac defect will evolve into hypoplastic left heart syndrome (HLHS) before birth (1,2). Fetal aortic valvuloplasty has been suggested as a method to prevent evolution into HLHS (2). Threshold criteria for this procedure have been developed from a single centers retrospective experience defining morphological and physiological characteristics of fetuses with aortic stenosis who had potential for a biventricular outcome following successful fetal valvuloplasty (2). Today, some centres have adopted the method into clinical practice (3) while others have been awaiting a higher level of evidence. Favourable results of fetal valvuloplasty have been reported from highly center-specific case series (3-6). Using the GRADE classification system, the level of evidence based on these reports is "very low" (+) (7,8). So far there has been only one observational study with a comparison cohort (9,10). In this study a benefit of valvuloplasty in terms of a greater proportion of cases being alive with a biventricular circulation at follow up could not be demonstrated. According to the GRADE system, the level of evidence of this study was higher than that of single center case series but still "low" (++). The limitations were several, including its retrospective design with self-reported echocardiographic data. The study covered an era when criteria for intervention was not yet definitely established and some of the participating interventional centers were in the early phase of their learning curve. The importance of these limitations was discussed by Friedman et al based on the Boston data (6).

To address the shortcomings of previous studies we are undertaking an international prospective observational cohort study with a comparison cohort to study the effect of fetal valvuloplasty in aortic stenosis.

## Paradigm

Fetal aortic valve stenosis may progress to left heart hypoplasia with univentricular circulation after birth. Fetal aortic valvuloplasty has been proposed, but not proven, as effective in maintaining biventricular circulation after birth.

#### Hypothesis

Fetal aortic valvuloplasty increases transplantation-free survival with a biventricular repair without pulmonary hypertension at 2 years postnatal age.

#### **Primary objective**

To evaluate if fetal valvuloplasty in aortic stenosis improves outcomes up to 2 years after birth compared with no fetal valvuloplasty, measured with transplantation-free survival from fetal diagnosis to 2 years postnatal age with a biventricular circulation without pulmonary hypertension at that time.

Absence of pulmonary hypertension is defined as a TR max velocity  $\leq 2.8$  m/s with no other echocardiographic signs of pulmonary hypertension and/or catheter data showing a mean pulmonary arterial pressure <25 mmHg (11,12).

#### Secondary objective

To evaluate fetal and maternal safety of fetal valvuloplasty.

Safety variables:

- Intervention-related fetal death (defined as fetal death within 24 hours of procedure).
- Fetal death not directly related to the intervention, except termination of pregnancy.
- Maternal complications to procedure (requiring intensive care or resulting in maternal death).
- Preterm delivery < 37 weeks.
- Fetal left heart growth from the point of study inclusion until just before the first postnatal catheter or surgical intervention

#### Study design

[figure not shown]
The study is an international multicenter prospective observational cohort study with a comparison cohort. Included are fetuses with a diagnosis of aortic stenosis who satisfy inclusion/exclusion criteria between 23+0 and 31+6 weeks of gestation. The decision whether a fetal balloon dilatation shall be attempted is not part of the study protocol. The number of examinations of mother/fetus/infant in this study is not different from the number of examinations that will be recommended for someone choosing not to be part of this study. The participation in the study is not affecting the treatment mothers and fetuses are receiving during pregnancy, nor how the infant is examined and treated after birth. The aim of the study

is to, in a prospective and organized way, collect and evaluate multi-center data in order to reduce the risk for selection bias, missing data and inter-variability between participating centers.

Cases will be recruited from centers offering fetal aortic valvuloplasty and and from centers not offering this treatment. Intervention cases will be recruited from high volume intervention centers. Fetal and postnatal echocardiographic examinations will be reviewed and remeasured by a core laboratory to confirm eligibility for inclusion, and identify potential measurement errors.

[figure not shown]
Data from two fetal echoes and one postnatal will be collected and each contains a comprehensive set of two-dimensional and Doppler measurements which will enable analysis of cardiac growth and development during pregnancy. Analysis of change of dimensions of the left heart structures and selected hemodynamic variables from the point of study inclusion until just before the first postnatal catheter or surgical procedure provides an opportunity to make a comparison between the groups that is unbiased with respect to centerspecific postnatal treatment policies.

Three echocardiographic examinations and a 2-year follow-up regarding patient outcome will be performed as per Figures 1-3 below.

## Figure 1. Study Overview – Fetal Protocols

## Figure 2. Study Overview – Neonatal Protocols

## Figure 3. Study Overview – Protocols at Follow-up at 2 Years of Age

Protocols at Follow-up at 2 years of age					
2	4 months	36 months			
	Follow-up at 2 years	s of age			
	eCRF 2 years follo	w-up			
eCRF F	Postnatal procedure(s) eCR	RF Subject termination			

#### Fetal aortic valvuloplasty

Fetal valvuloplasty will be performed as previously described (3) with minor variations between centers involved. Technical success is defined as improved forward flow and/or new aortic regurgitation.

#### **Echocardiographic examinations**

There are three echocardiographic examinations in the study:

1. Baseline fetal echo at 23+0 to 31+ 6 weeks of gestation.

2. Follow-up fetal echo at 33 + 0 to 34 + 6 weeks of gestation.

3. The first complete echocardiographic examination after birth (before the first postnatal intervention).

#### **Z**-scores

Z-scores for fetal cardiac measurements will be derived by gestational age (13, 14). Gestational age is automatically calculated by the eCRF system using the equation Gestational Age = (280 - (EDD - Reference Date)) / 7.

Z-scores for postnatal cardiac measurements will be derived by body surface area (15, 16).

#### Echocardiographic data

Echocardiographic data will be used for:

1. Inclusion criteria (baseline fetal echo).

2. Longitudinal assessment of cardiac growth and hemodynamics (baseline fetal echo, follow-up fetal echo and postnatal echo before first postnatal procedure).

#### **Inclusion criteria**

The inclusion criteria will be identical in the intervention and the non-intervention cohorts. A modification of the inclusion criteria published by the group in Boston (2) and by the group in Linz (3) will be used. The modification is based on the retrospective study (9,10) and represent the currently used criteria for intervention.

- A. All of the following echocardiographic criteria need to be satisfied between 23+0 and 31+6 weeks (z-scores according to Schneider et al (13)):
- 1. Aortic valve stenosis with antegrade flow through the valve
- 2. Predominantly left-to-right shunt at the atrial level

- 3. Predominantly retrograde flow in the aortic arch between the first two brachiocephalic vessels
- 4. Qualitatively depressed left ventricular function
- 5. LV end-diastolic diameter Z-score  $> \pm 0$
- 6. Left ventricular inlet length in diastole :
  - a. Gest age  $\leq 24+6$ : Z-score  $> \pm 0$
  - b. Gest age 25+0 to 27+6: Z-score > -0.75
  - c. Gest age  $\geq 28+0$ : Z-score > -1.50
- 7. Mitral valve diameter in diastole Z-score > -2.0
- B. All of the following postnatal treatment options need to be available:
  - 1. Surgical or catheter based aortic valvotomy
  - 2. Ross-Konno surgery
  - 3. Norwood or hybrid stage-one surgery

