## Electronic case report forms (eCRF)

There are 14 eCRF's:

1. eCRF Inclusion criteria

All inclusion and no exclusion criteria need to be satisfied for a case to be included.

2. eCRF Inclusion

Include case if inclusin/exclusion criteria satisfied.

3. eCRF Counselling on fetal aortic valvuloplasty

If councelling was performed and, if so, what the decision was.

4. eCRF Baseline fetal echo 23+0 - 31+6

The baseline fetal echo is performed between 23+0 and 31+6 weeks. If an intervention is performed, the last exam before the intervention should be used as baseline fetal echo.

5. eCRF Additional baseline fetal echo 23+0 - 31+6

In case there is a late descision to perform an intervention, after a baseline fetal echo has already been submitted, there is an option to add an additional baseline fetal echo in the system.

6. eCRF Fetal interventions

A new eCRF Fetal interventions should be added for each intervention performed.

7. eCRF Follow-up fetal echo 33+0 - 34+6

The follow-up fetal echo is performed between 33+0 and 34+6 weeks.

8. eCRF Neonatal - Birth

Gestational age and size at birth, mode of delivery and pharmacological support.

9. eCRF Neonatal - Echo

First full study after birth, and before the first postnatal intervention, surgery or cath (except emergency atrial septostomy)

10. eCRF Neonatal - Cardiac clinical diagnosis

Cardiac diagnoses before the first intervention, surgery or cath (except emergency atrial septostomy)

11. eCRF Neonatal - Neonatal discharge

Type of circulation and clinical diagnoses at discharge.

12. eCRF Follow-up at 2 years of age

Type of circulation, clinical diagnoses, pulmonary hypertension, neurological sequealae, somatic growth.

13. eCRF Postnatal procedures

All cardiac surgical and catheter interventional procedures from birth to 2 years follow-up

14. eCRF Subject termination

Reason for subject termination including completion at 2 years of age.

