### Data analysis and statistical support

The main analysis comparing intervention versus non-intervention will be on an intention-totreat, i.e. intention to perform fetal aortic valvuloplasty, basis. Intention to perform fetal valvuloplasty is defined as being present if the needle has been introduced through the maternal abdominal wall even if the fetal thorax has not been touched. Subjects will be identified as belonging to the fetal aortic valvuloplasty (FAV) or the no-FAV groups as listed below.

The following study groups will be identified:

- Subjects that undergo a technically successful fetal aortic valvuloplasty at a high volume intervention centre (FAV 1).
- Subjects with intention-to-treat (according to the above definition) at a high volume intervention centre but with no technical success (FAV 2).
- Subjects counselled at a center not performing or referring for fetal aortic valvuloplasty (no-FAV 1).
- Subjects counselled at a high- or low-volume intervention center, or at a center offering referrals to a center performing interventions, and the parental decision is to not perform fetal aortic valvuloplasty (no-FAV 2).

The main analyses will be to compare FAV 1+2 versus no-FAV 1+2. The expected proportion of enrolled fetuses/infants will be 2 [FAV] : 1 [no-FAV]. Complementary analyses will be comparing FAV 1 versus no-FAV 1, and FAV 1 versus no-FAV 1+2.

Statistical support will be provided by Statistiska Konsultgruppen, Gothenburg, Sweden ([name]). Sample size will be calculated based on our previous retrospective study in combination with results published by the Boston group and by IFCIR (International Fetal Cardiac Intervention Registry).

The main analysis will be on an intention-to-treat basis. In this analysis fetal intervention cases, regardless of whether the intervention was technically successful or not, will be compared with non-intervention cases with regard to the primary outcome measure. Cox proportional hazards regressions and Kaplan Meier curves will be constructed, comparing survival between cohorts. Fetal left heart growth will be analyzed using descriptive statistics and will be compared between intervention and non-intervention groups from baseline fetal echo to the follow-up fetal and neonatal echo respectively.

In additon the same comparisons will be made after excluding the technically unsuccessful cases.

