1.4 Study Groups

The main analysis comparing intervention versus non-intervention will be on an intention-totreat, i.e. intention to perform fetal aortic valvuloplasty, basis. Intention to perform fetal valvuloplasty is defined as being present if the needle has been introduced through the maternal abdominal wall even if the fetal thorax has not been touched. Subjects will be Protocol

Statistical Analysis Plan

1.0

identified as belonging to the fetal aortic valvuloplasty (FAV) or the no-FAV groups as listed below.

The following groups will be identified:

- Subjects that undergo a technically successful fetal aortic valvuloplasty at a high volume intervention centre (FAV 1).
- Subjects with intention-to-treat (according to the above definition) at a high volume intervention centre but with no technical success (FAV 2).
- Subjects counselled at a center not performing or referring for fetal aortic valvuloplasty (no-FAV 1).
- Subjects counselled at a high- or low-volume intervention center, or at a center offering referrals to a center performing interventions, and the parental decision is to not perform fetal aortic valvuloplasty (no-FAV 2).

The main analyses will be to compare FAV 1+2 versus no-FAV 1+2. The expected proportion of enrolled fetuses/infants will be 2 [FAV] : 1 [no-FAV]. Complementary analyses will be comparing FAV 1 versus no-FAV 1, and FAV 1 versus no-FAV 1+2.

Figure 4. Main and complementary analysis

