2.1.4 Per-Protocol Population for Live Births Intended for Postnatal Treatment

All enrolled fetuses that are *live at birth and intended for treatment* with no major protocol violations will be included in the Per Protocol at birth (PP_{BIRTH}) population. The final decisions

Statistical Analysis Plan

Protocol No:

regarding the PP_{BIRTH} population will be taken at the Clean File meeting before the database lock.

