3.4 Efficacy Variables

3.4.1 Primary Efficacy Variable

The primary efficacy variable is transplantation-free survival until 2 years postnatal age, having a biventricular circulation without pulmonary hypertension at that time. Diagnosis of pulmonary hypertension will be based on catheter/echo/clinical data and graded as mild, moderate or severe. This means that death, transplantation and biventricular circulation with pulmonary hypertension or no biventricular circulation will be part of this composite endpoint coded as yes/no. This variable cannot be analysed as time to event variable due to the fact that biventricular circulation and pulmonary hypertension are evaluated at 2 years of age. Early discontinuations for other reasons than death, without transplantation and with biventricular circulation without pulmonary hypertension at the time of early discontinuation will be counted in no event group.

The primary variable will be analysed on FAS_{ENR} (main analysis), FAS_{BIRTH}, PP_{ENR} and PP_{BIRTH}, overall for FAV 1+2 vs no-FAV 1+2 (main analysis), and descriptively FAV 1 vs no-FAV 1 and FAV 1 vs no-FAV 1+2.

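### Eligibility asks whether postnatal treatment is available, not whether the family intends it; fetuses with no treatment planned probably fall mainly in no-FAV, stay in the confirmatory set as failures, and tilt the comparison towards FAV.

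*Protocol*

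**What the plan says.** **Eligibility.** Criterion B (Protocol, Inclusion criteria; SAP 1.3.1) reads "All of the following postnatal treatment options need to be available", followed by three surgical or catheter options. No inclusion or exclusion criterion concerns the family's plan for the newborn.

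**Groups.** A fetus is in FAV "if the needle has been introduced through the maternal abdominal wall even if the fetal thorax has not been touched" (SAP 1.4). The comparison groups are "Subjects counselled at a center not performing or referring for fetal aortic valvuloplasty (no-FAV 1") and those counselled where FAV is performed or referral is offered, when "the parental decision is to not perform fetal aortic valvuloplasty (no-FAV 2"). Postnatal plans appear in none of these definitions.

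**What is recorded.** The protocol describes eCRF 3, on counselling about FAV, as "If councelling was performed and, if so, what the decision was". Intention to treat is listed in SAP 3.2 as a neonatal variable. It is not among the inclusion and baseline variables of SAP 3.1, from which the potential confounders are drawn.

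**Endpoint and sets.** SAP 3.4.1 states that "death, transplantation and biventricular circulation with pulmonary hypertension or no biventricular circulation will be part of this composite endpoint coded as yes/no". The confirmatory analysis is on FAS_ENR, FAV 1+2 against no-FAV 1+2 (SAP 4.1, 4.6.1). PP_BIRTH is limited to fetuses "live at birth and intended for treatment" (SAP 2.1.4). The heading of SAP 2.1.2 (FAS_BIRTH) also refers to intended postnatal treatment, but the definition beneath it requires only live birth. Both at-birth sets are complementary. The protocol excludes terminations after inclusion from analysis.

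**The concern.** The plan foresees newborns who will not be treated, since it records intention after birth and builds one analysis set on it. The confirmatory set has no such filter.

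Agreeing to an invasive fetal procedure meant to preserve a postnatal biventricular circulation is itself an informal filter on intention. No-FAV has no equivalent. In no-FAV 2, a decision against postnatal treatment may be the reason FAV was declined. In no-FAV 1 there was no offer to decline, but nothing screens such families out either.

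A fetus born with no treatment planned has essentially no chance of meeting the primary endpoint, whether or not FAV works. An excess of these in no-FAV moves the odds ratio towards FAV. The adjusted model uses confounders available at inclusion, and the propensity score draws on the same data. Heart measurements, gestational age and maternal BMI do not stand in for parental intention, so neither method can remove the imbalance.

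**Working it through.** **Inputs from the documents** (Protocol, Sample size; SAP 1.5): 100 FAV, 50 no-FAV, alpha 0.05, two-sided Fisher's exact test, planned success 30% in no-FAV and 60% in FAV.

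**Inputs assumed:** q is the share of no-FAV with no postnatal treatment planned at inclusion and the pregnancy continued to birth. The documents do not give it; 5% to 30% is shown. s is the success rate among fetuses intended for treatment, equal in both arms (no true FAV effect). Success is zero without treatment. FAV holds no such fetuses unless stated.

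**The plan's own figure.** Full enumeration of both binomials for 60% vs 30% at 100:50 gives power 92.7%. The plan states 91.8%, so it is reproduced to within one point.

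**Formulas.**
- Observed no-FAV success = s(1−q)
- Bias in the risk difference = s − s(1−q) = q·s
- Odds ratio = [s/(1−s)] / [s(1−q)/(1−s(1−q))]

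Example with s=0.30 and q=0.20: no-FAV success is 0.30×0.80=0.24, and the odds ratio is (0.30/0.70)/(0.24/0.76)=0.4286/0.3158=1.36. In counts, 10 of 50 no-FAV fetuses are affected and 10×0.30=3 expected successes are lost.

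**Results.** False significance means the probability that the Fisher test rejects in favour of FAV when FAV has no effect.

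| Scenario | Quantity | q=0 | q=5% | q=10% | q=20% | q=30% |
|---|---|---|---|---|---|---|
| s=30% (planned no-FAV rate, all treated) | no-FAV success | 30% | 28.5% | 27% | 24% | 21% |
| | odds ratio | 1.00 | 1.08 | 1.16 | 1.36 | 1.61 |
| | false significance | 1.9% | 3.0% | 4.5% | 9.6% | 18.5% |
| planned 30% already includes them, s=0.30/(1−q) | s | 30% | 31.6% | 33.3% | 37.5% | 42.9% |
| | odds ratio | 1.00 | 1.08 | 1.17 | 1.40 | 1.75 |
| | false significance | 1.9% | 3.1% | 4.9% | 12.8% | 30.7% |
| s=45% | odds ratio | 1.00 | 1.10 | 1.20 | 1.45 | 1.78 |
| | false significance | 2.0% | 3.7% | 6.4% | 16.1% | 32.9% |

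**Such fetuses in both arms.** With s=45%, 5% in FAV and 20% in no-FAV, success is 0.45×0.95=42.75% vs 0.45×0.80=36%. The odds ratio is 1.33 and false significance is 10.6%, against 16.1% when FAV holds none.

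**Limit of the calculation.** The Fisher test is unadjusted, as in the plan's own power calculation; the confirmatory test is an adjusted logistic regression. Adjustment would change these figures somewhat, but it cannot remove an imbalance in a factor it does not contain.

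**The case against.** Several objections have force.

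- **One arm only.** A reader might infer that only no-FAV can hold such fetuses. The documents do not support that. FAV membership depends on needle entry alone, no rule bars these families, and a FAV family may decline postnatal treatment later. Mainly no-FAV is as far as the text and ordinary reasoning go.
- **Declining as the mechanism.** This applies to no-FAV 2, which the plan expects to be probably the smaller comparison group. The planned FAV 1 vs no-FAV 1 comparison removes decliners. It is descriptive, however, it drops technical failures from FAV, and it leaves any untreated births within no-FAV 1.
- **Terminations.** Under the protocol these leave the analysis, so one route to non-treatment is not scored as failure. That narrows q to pregnancies continued to birth.
- **Size.** q has no source. At 5% the effect is small under all three scenarios (3.0% to 3.7%), and it becomes large only towards 30%.
- **Existing sets.** PP_BIRTH does remove untreated newborns. But it is complementary, conditions on live birth and so drops fetal deaths, and uses intention known after birth, which FAV may itself have influenced. FAS_BIRTH would help only if its definition followed its heading.
- **Unseen material.** The annotated eCRF was not supplied, and Figures 5 and 6 are not shown. If intention at inclusion is already collected, only the SAP needs to change.

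These limit the certainty and size of the point. They do not remove the gap in the confirmatory analysis.

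**Conclusion.** The point holds as a plausible, uncorrected baseline imbalance that favours FAV. Criterion B tests availability only, untreated births remain in FAS_ENR as failures, and no listed variable captures intention at inclusion.

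At the plan's 30% rate, the chance of a false finding for FAV rises from 1.9% to between 3.0% and 18.5% for q of 5% to 30%. If the planned 30% already contains these fetuses, the range is 3.1% to 30.7%. This rests on no true FAV effect, zero success without treatment, none in FAV, an unadjusted Fisher test and an assumed q.

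A reader might go further and infer that any FAV benefit the study reports would be the product of parental intention. The documents do not support that. The bias is q·s, not q, because at s=30% seven in ten of these fetuses would have failed anyway. To produce the whole planned gap of 60% vs 30% in this way, 0.60(1−q)=0.30 would be needed, that is q=50%.

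Separately, the heading and definition of FAS_BIRTH disagree and must be reconciled.

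**What to change.** 1. Add one eCRF field, completed at the inclusion visit in both arms and before the FAV decision or any needle entry: active postnatal treatment intended, with answers yes, undecided or no. The timing must be the same in both arms. If it were recorded later in no-FAV, later scans could influence the answer there only.
2. In SAP 4.6.1, prespecify a sensitivity analysis of the primary logistic model in FAS_ENR restricted to yes or undecided, and a second restricted to yes.
3. Report per arm the number answering no and the number of live births not treated.
4. Reconcile the heading and definition of FAS_BIRTH in SAP 2.1.2.

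Redefining FAS_ENR itself on intention is optional for the sponsor. There is a parallel in SAP 2.1.1, which removes the high-risk fetuses because they are likely to be over-represented in FAV to a degree that propensity matching could hardly control.

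The cost is one field, one or two extra model runs and some SAP wording. The restricted set also has fewer no-FAV fetuses. If the planned 30% includes untreated births, unadjusted power for 60% in FAV falls from 92.7% to 84.8% at q=10% (45 no-FAV, 33.3% success), 64.2% at q=20% (40, 37.5%) and 39.6% at q=30% (35, 42.9%). The restricted result should therefore be read mainly by its estimate and interval. Clinical care does not change.
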